6.15 Appropriateness of Measurements

Measurements to be performed during the course of the study (with the following exceptions) are standard for the indication or patient population under study: testing for phytosterols and genetic polymorphisms, while not standard, are appropriate for addressing the study endpoints.

7. STUDY ACTIVITIES

The details of the schedule of events are provided in Appendix 1, Schedule of Events Table.

7.1 Screening Period

After providing written IC, patients will enter the Screening Period. The Screening Period is defined as the period after the ICF is signed and dated until randomization. The maximum duration of this period is 3 days prior to dosing. Randomization is recommended within 24 hours of signing consent but must occur within 3 days of signing consent. If patient is not randomized within 24 hours of informed consent, patient should be started on SOC ILE on Day 1 of PN as per Table 4 and Section 5.3. Signing and dating of the ICF and the Screening visit may occur on the same day, if necessary; however, the ICF must be signed and dated before any Screening activities can be conducted.

The aim of the Screening Period is to determine the eligibility (inclusion/exclusion criteria) of patients for randomization.

Further assessments conducted during Screening include:

- Demographics
- Gestational age and birth weight for infants <1 years of age only
- Medical history (including diagnosis requiring PN)
- Physical examination, including weight and length or height (and head circumference for infants <1 year of age)
- Vital signs
- Laboratory evaluations including hematology and chemistry (refer to Appendix 1, Schedule of Events Table)
- Pregnancy test. Note: All female patients ≥12 years of age must have a negative urine human chorionic gonadotropin (hCG) pregnancy test at screening. For female patients <12 years of age, a urine hCG test at screening will be performed at the discretion of the investigator based on childbearing potential.
- Nutritional intakes
- Medication history
- Randomization to study treatment
- Adverse Events (AEs occurring during Screening but prior to administration of study treatment will be considered as unrelated to study treatment). Non-serious AEs during this time period will be collected as part of the medical history. Serious adverse events will need to be reported as per Section 6.13.7.2.

7.2 Study Treatment Period (Baseline to Day 90)

7.2.1 Baseline Procedures

Baseline is defined as the period within ± 24 hours of first study treatment administration. The following procedures will be performed at Baseline (≤ 24 hours prior to administration of study treatment):

- Medical history will be updated as necessary.
- Physical examination including weight and length or height (and head circumference for infants <1 year of age)
- Vital signs
- Nutritional intakes
- Concomitant medications
- Concomitant procedures
- AEs

The following laboratory procedures will be performed at Baseline (± 24 hours prior to administration of study treatment). Baseline laboratory assessments need not be repeated if completed within 24 hours of screening sampling:

- Laboratory evaluations including (refer to Appendix 1, Schedule of Events Table):
 - Hematology and chemistry
 - Hepatic function tests
 - Triglycerides
 - Fatty acid profile
 - Holman Index
 - Phytosterol, cholesterol, and squalene levels

Buccal swab samples for the determination of genetic polymorphisms for FADS1 (rs174553) and FADS2 (rs174575, rs99780, rs174583) will be collected from all enrolled patients for whom consent is obtained. Buccal swabs can be collected at any time before the end of study treatment.

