6.7.2.4 Fatty acid profiles, Holman Index, and phytosterol, cholesterol, and squalene levels

Blood samples for the determination of FA profiles, Holman Index, and phytosterol (stigmasterol, campesterol, sitosterol), cholesterol, and squalene levels will be collected at Baseline from all patients enrolled in the study. Subsequent samples for FA profiles will be collected on an approximately 15-day basis at least 4 hours after interrupting ILE infusion in order to decrease the influence of infused ILE on FA profile. If a study site typically infuses ILE over 24 hours, the investigator should, to the best of their ability,

ensure a 4-hour lipid only infusion hold before obtaining samples for the FA profiles. Ongoing infusion of other macro- and micronutrients from PN are allowed as required for the best interest of the patient per the attending physician during the 4-hour ILE hold before obtaining samples for the FA profiles. Blood sample volumes will be kept to a minimum.

Blood samples for FA profiles, determining Holman Index, and quantifying the amount of phytosterols, cholesterol, and squalene in samples will be processed by an external laboratory. The FAs will be assessed according to the Mayo Clinic method, which is performed as a 2-step acid-base hydrolysis followed by hexane extraction and derivatization with pentafluorobenzyl bromide. Separation and detection are accomplished by capillary gas chromatography electron-capture negative ion-mass spectrometry. Quantitation is based on analysis in the selected ion-monitoring mode by using 13 stable isotope-labeled internal standards. Handling, labeling, and shipping procedures will be detailed in separate Laboratory Instructions provided by the Sponsor.

Reference values can be found in Appendix 2.

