Appendix 1 Schedule of Events Table

Evaluation	Evaluation Screening Baseline ^a Dai		Daily	Study Treatment Day (every 15 days ±2 days)					End of Study Treatment ^o
				15	30	45	60	75	or Day 90 (± 2 days)
Informed consent / assent (as applicable)	X								
Confirm eligibility	X								
Randomization ^b	Х								
Demographics ^c	Х								
Medical history including diagnosis for requiring PN	Х	Х							
Physical examination including length or height and head circumference	X	Х		X	X	X	Х	X	Х
Body weight ^d	Х	Х	Х	Х	Х	Х	Х	Х	Х
Vital signs ^e	Х	Х	Х	Х	Х	Х	Х	Х	Х
Diagnosis of neonatal morbidities ^f									Х
Laboratory Evaluations									
Hematology and serum chemistry	Х	Х	Standard-of-Care and every 15 days ± 2 days						
Triglyceride levels	X	Х	Standard-of-Care and every 15 days ±2 days						
Hepatic function tests	Х	Х	Stand	ard-o	f-Car	e and	ever	y 15 a	days ±2 days
Fatty acid profile and Holman Index ^g		Х		Х	Х	Х	Х	Х	Х
Genetic polymorphism sample (buccal swab) ^h		Х							
Phytosterol, cholesterol, and squalene levels ⁱ		Х		Х	Х	Х	х	Х	Х
Human chorionic gonadotropin (hCG) ^j	X								
Nutritional Intake									
PN lipid intake ^k		X	X	Х	Χ	Χ	Х	Х	X
Other macronutrient PN intake		Х	Х	Х	Х	Х	Х	Х	Х
Breast milk intake ¹	X	Х	Х	Х	Х	Х	Х	Х	Х
Enteral formula intake	X	Х	Х	Χ	Χ	Х	Χ	Х	X

Evaluation	Screening Baseline ^a		Daily	Study Treatment Day (every 15 days ±2 days)				End of Study Treatment ^o	
				15	30	45	60	75	or Day 90 (± 2 days)
Oral food intake	Х	Х	Х	Х	Х	Х	Х	Х	Х
Concomitant medications / nutritional supplements ^m	Х	Х	Х	Х	Х	Х	Х	Х	Х
Concomitant procedures	Х	Х	Х	Х	Х	Х	Х	Х	Х
Adverse events ⁿ	Х	Х	Х	Χ	Χ	X	Χ	Χ	Х

PN=parenteral nutrition

^a Baseline evaluations should be done \leq 24 hours before first study treatment administration, however, baseline laboratory assessments may be done within ±24 hours of first study treatment administration. Baseline tests need not be repeated if within 24 hours of screening sampling. Buccal swabs can be collected at any time before the end of study treatment.

^b Randomization is recommended within 24 hours of signing consent but must occur within 3 days of signing consent (section 7.1)

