^c For all neonates (premature infants born <37 weeks of gestation up to 1 month CA and full-term neonates <1 month of age), gestational age (GA) will be recorded at Screening and categorized as full-term (born \geq 37 weeks of gestation), preterm (32-36 weeks of gestation), very preterm (28-31 weeks of gestation), or extremely preterm (<28 weeks of gestation).

^d Including weight and length or height (and head circumference for infants <1 year of age). For all neonates (premature infants born <37 weeks of gestation up to 1 month CA and full-term neonates <1 month of age), BW will be recorded at Screening and categorized as normal BW (≥2500 g), low BW (1500-2499 g), very low BW (1000-1499 g), or extremely low BW (<1000 g).

^e Vital signs will be collected once daily at approximately the same time each day (e.g. 8 AM), with a window of approximately 2-3 hours. Vital signs include heart rate (beats/min), respiratory rate (breaths/min), systolic and diastolic blood pressure (mmHg), and body temperature (°C).

^f Diagnosis of neonatal morbidities diagnoses including BPD, ROP, IVH, PVL, NEC, and late-onset sepsis in enrolled premature and low birth weight neonates. Diagnostic criteria and severity grading will be per standard-of-care.

^g Samples are to be collected \geq 4 hours after completing last lipid infusion. Samples are to be collected at the same time every day.

- ^h Buccal swab samples for the determination of genetic polymorphisms for FADS1 (rs174553) and FADS2 (rs174575, rs99780, rs174583) will be collected from all enrolled patients for whom consent is obtained. Buccal swabs can be collected at any time before the end of study treatment. Buccal swabs will be destroyed once all analyses have been completed.
- ⁱ Clarification on laboratory measurements will be provided in a separate laboratory manual.
- ^j All female patients ≥12 years of age must have a negative urine human chorionic gonadotropin (hCG) pregnancy test at screening. For female patients <12 years of age, a urine hCG test at screening will be performed at the discretion of the investigator based on childbearing potential.

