2.1.1 Definition of baseline

Unless otherwise specified, baseline is defined as the values collected at the baseline visit. The value closest to the start of treatment will be used for baseline if multiple values (e.g. laboratory re-tests) are available. If the value at baseline is missing, then the value at the screening visit will be used as baseline.

Any medical condition that is present at the time that a participant is screened will be considered baseline medical history and will not be reported as an adverse event.

Change from baseline variables will be calculated as the post-treatment value minus the value at baseline.

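### The baseline fatty-acid, Holman Index and sterol sample may be drawn up to 24 hours after randomised lipid starts, and SAP 2.1.1 does not require a pre-dose value

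*Protocol*

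**What the plan says.** Protocol 7.2.1 opens with a two-sided window: "Baseline is defined as the period within ± 24 hours of first study treatment administration". It then treats two groups of procedures differently. For examination, vital signs, intakes and the like it is one-sided: "The following procedures will be performed at Baseline (≤ 24 hours prior to administration of study treatment". For laboratory work it reads "The following laboratory procedures will be performed at Baseline (± 24 hours prior to administration of study treatment", and the list that follows includes the fatty-acid profile, Holman Index, phytosterols, cholesterol and squalene. A plus-or-minus window cannot also be wholly prior, but footnote a of Appendix 1 settles the meaning: "baseline laboratory assessments may be done within ±24 hours of first study treatment administration". The same footnote stands in the schedule in SAP 1.4.5.

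For analysis, SAP 2.1.1 takes the baseline-visit value, with this rule for duplicates: "The value closest to the start of treatment will be used for baseline if multiple values (e.g. laboratory re-tests) are available". Its fallback is "If the value at baseline is missing, then the value at the screening visit will be used as baseline".

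On sampling conditions, Protocol 6.7.2.4 says "Subsequent samples for FA profiles will be collected on an approximately 15-day basis at least 4 hours after interrupting ILE infusion". Footnote g, attached to the fatty-acid and Holman row including its Baseline column, asks for samples at least 4 "hours after completing last lipid infusion". The phytosterol, cholesterol and squalene row does not carry footnote g. It carries footnote i, which points to a laboratory manual.

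**The concern.** A baseline should describe the patient before the randomised product can act. Here the central-laboratory sample may follow as much as a day of that product, and the two products differ in the very substances being measured. Nothing in SAP 2.1.1 prevents a post-dose value from serving as baseline. The screening fallback cannot supply a pre-dose value, because these tests are first scheduled at Baseline.

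Two things are at stake. One is the baseline summary of sterols and squalene by arm (SAP 2.4.2.4), which may already differ because of treatment. The other is how an early high Holman Index is classified. Protocol 9.3 sets infants with baseline EFAD apart and does not count them as treatment-emergent, and Protocol 6.8.4 expects such infants, especially among the premature. SAP 2.4.1.1 counts any value above 0.4 during study treatment as an event. A sample taken 12 hours after the start fits both descriptions.

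**Working it through.** **Check of the protocol's own composition figures.** Both emulsions contain 0.2 g lipid per mL, so 100 g of lipid is 500 mL. Total phytosterols from Protocol Table 2:
- Intralipid: 439.07 µg/mL × 500 mL = 219.5 mg (the table gives 220)
- Clinolipid: 274.38 µg/mL × 500 mL = 137.2 mg (the table gives 137)

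The figures are consistent.

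**Randomised product that can precede a baseline sample.** The limit of the window is +24 h. At the Day 1 dose in Table 4, 1 g/kg ÷ 0.2 g/mL = 5 mL/kg. Amount infused = content × 5 mL/kg.

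| Substance | Clinolipid | Intralipid |
|---|---|---|
| Squalene | 387.45 × 5 = 1,937 µg/kg (1.94 mg/kg) | 7.43 × 5 = 37 µg/kg (0.04 mg/kg) |
| Total phytosterols | 274.38 × 5 = 1,372 µg/kg (1.37 mg/kg) | 439.07 × 5 = 2,195 µg/kg (2.20 mg/kg) |
| Stigmasterol | 12.15 × 5 = 61 µg/kg | 65.05 × 5 = 325 µg/kg |
| Linoleic acid | 18.6% × 1 g/kg = 0.186 g/kg | 54.7% × 1 g/kg = 0.547 g/kg |

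The squalene ratio is 387.45 ÷ 7.43 = 52. With the mean linoleic acid content in Protocol 5.1.1 (35.8 mg/mL) the Clinolipid figure is 0.179 g/kg, which changes nothing. Protocol 5.3 lets patients already on standard-of-care lipid continue their progression. At the table maximum of 3 g/kg/day all these amounts triple (squalene 5.81 against 0.11 mg/kg).

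**How much room footnote g leaves.** Infusions run 20 to 24 h (Table 4, note a). Adding 4 h gives 24 to 28 h after the start. If footnote g governs baseline, a post-dose fatty-acid or Holman draw after a completed infusion fits only at the +24 h limit, by which time a full day's dose has been given. An earlier one requires an interrupted infusion. If only 6.7.2.4 governs, the hold is stated for later samples and a baseline could be drawn mid-infusion. The sterol row has no such limit in the schedule.

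**What one doubly classified patient is worth.** In a planned arm of 50, one patient moved into or out of the EFAD count changes the proportion by 1 ÷ 50 = 2 percentage points. It is more if fewer than 50 have a post-baseline Holman Index, which is the denominator in SAP 2.4.1.2.

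**The case against.** The strongest counter-argument concerns the primary analyte. Footnote g sits on the Holman row at baseline too, and 6.7.2.4 does not exempt baseline in so many words. Read that way, the post-dose window is nearly shut. The schedule also provides a single baseline draw and Protocol 6.7.2.4 wants blood volumes kept small, so the closest-value rule is a tie-breaker for re-tests and will seldom operate. It is not a general preference for post-dose values. All this stands. It does not help the sterol row, although the laboratory manual, which is not among the documents, may set conditions there.

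A reader might go further and infer three things that the documents do not support.
- *That true baseline EFAD status is lost.* The figures above are infused amounts, and no document says how far a plasma Holman Index moves in 24 hours. The only timing evidence, in Protocol 6.8.3, asks for at least a week of increased linoleic acid intake before the profile is repeated.
- *That the change on treatment is understated.* The SAP plans no change from baseline for the Holman Index, fatty acids or sterols (2.4.1.2, 2.4.2.4). The delay from baseline to maximum could move by about a day.
- *That per-protocol membership is biased.* SAP 1.5.1 requires only that a baseline Holman measurement exists; its value plays no part.

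The study is also descriptive, with no hypothesis tests and no covariate adjustment, which limits how far any distortion can travel.

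**Conclusion.** The concern holds as a gap in the definition of baseline. The permission to sample after dosing is explicit and repeated in both documents, and SAP 2.1.1 does nothing to counter it. A possible arm effect at baseline is clearest for squalene (a 52-fold difference in content) and next for phytosterols. For the Holman Index its size cannot be computed from the documents and the opportunity may be small. What remains there is the double reading of a post-dose value above 0.4 under Protocol 9.3 and SAP 2.4.1.1, which needs settling whether or not the index moves within a day.

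This rests on the content figures in Protocol Tables 1 and 2 (the sterol figures come from a single lot), on the Table 4 doses, and on the schedule as printed. How many patients are sampled after dosing is not stated; the rule permits it for any of them, which says nothing about how often it happens.

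**What to change.** 1. SAP 2.1.1: for the fatty-acid profile, Holman Index, phytosterols, cholesterol and squalene, define baseline as the last sample before the start of study treatment. This needs the time of the draw as well as its date.
2. SAP 2.1.1 and 2.4.1.1: where the only baseline-visit sample is post-dose, flag it and list it by arm, do not count it as an incident EFAD event, and repeat the EFAD and baseline sterol summaries without those patients. Simply relabelling such a sample as post-baseline would be wrong, because EFAD present before treatment would then count as an event.
3. Protocol 7.2.1 and footnote a (and its copy in SAP 1.4.5): require this one central-laboratory draw before first study treatment.
4. Reconcile Protocol 6.7.2.4 with footnote g so that baseline and later samples are taken under the same infusion condition.

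The cost is less flexibility in the timing of one draw, and a few patients without a valid pre-dose baseline. SAP 1.5.1 should say whether those patients stay in the per-protocol set. Items 1 and 2 use samples already collected and need no extra blood, provided draw times are recorded.

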7.2.2 Daily Procedures

The following procedures will be performed and recorded in the CRF on a daily basis during the Study Treatment Period.

- Weight
- Vital signs
- All nutritional intakes
- Concomitant medications
- Concomitant procedures
- AEs

7.2.3 Standard-of-Care Procedures

The following procedures will be performed at intervals determined by the SOC at each investigational site (refer to Appendix 1, Schedule of Events Table):

- Laboratory evaluations including:
 - hematology complete blood count
 - chemistry basic metabolic panel and electrolytes
- Diagnosis of neonatal morbidities including bronchopulmonary dysplasia (BPD), retinopathy of prematurity (ROP), intraventricular hemorrhage (IVH), periventricular leukomalacia (PVL), necrotizing enterocolitis (NEC), and late-onset sepsis in enrolled premature infants born at 24 to <37 weeks of gestation up to 1 month CA with a birth weight ≥750g.

7.2.4 Days 15, 30, 45, 60, 75 and 90 or End of Study Treatment Procedures

The Study Treatment Period starts when the patient receives study treatment. End of study treatment is defined as the last day of PN with Intralipid or Clinolipid; maximum 90 days of study treatment is allowed.

The following procedures will be performed approximately every 15 days ± 2 days for patients continuing on PN (days 15, 30, 45, 60, 75 and 90) and within ± 2 days of the last day of study treatment (maximum 90 days on either Clinolipid or Intralipid) whenever that occurs:

- Physical examination including weight, length or height (and head circumference for infants <1 year of age)
- Vital signs
- Concomitant medications
- Concomitant procedures
- AEs
- Laboratory evaluations including:
 - Hematology parameters
 - Serum chemistry parameters
 - Hepatic integrity parameters
 - Total and direct bilirubin
 - Triglyceride levels
 - FA profile
 - Holman Index
 - Phytosterol, cholesterol, and squalene levels

In addition, the following data will be collected at end of study treatment:

 Diagnosis of neonatal morbidities including bronchopulmonary dysplasia (BPD), retinopathy of prematurity (ROP), intraventricular hemorrhage (IVH), periventricular leukomalacia (PVL), necrotizing enterocolitis (NEC), and lateonset sepsis in enrolled premature infants born <37 weeks of gestation up to 1 month CA.

After end of study treatment (maximum of 90 days), the patient will receive nutritional intervention as prescribed by their healthcare provider as SOC if PN is still required.

8. QUALITY CONTROL AND ASSURANCE

The Sponsor is responsible for implementing and maintaining quality assurance and quality control systems with written SOPs to ensure that studies are conducted and that the data are generated, documented, and reported in compliance with the protocol and applicable regulatory requirements. Quality control will be applied to all stages of data handling to ensure reliability and correct processing. The Sponsor or designee is

responsible for securing agreement from all involved parties to ensure direct access to all study-related centers, source documents, and reports for the purpose of monitoring and auditing. Agreements made with the Investigator/institution will be in writing.

This study may be subject to an independent audit at the investigational study center, which will be conducted by the Sponsor's quality assurance personnel or designee. Full consultation with appropriate personnel will be made before and during such an audit. The Investigator must be available during the audit. If the Investigator is contacted by any regulatory authority regarding an audit for this study, the Investigator must contact the Sponsor immediately.

9. PLANNED STATISTICAL METHODS

9.1 General Considerations

A more detailed description of the statistical analysis will be presented in the Statistical Analysis Plan (SAP).

9.2 Determination of Sample Size

The sample size of 100 patients (50 in each of the 2 treatment groups: Clinolipid vs Intralipid), including neonates, is based on the feasibility of timely enrollment of patients for generating reference data and summary descriptive statistics, rather than on a formal power calculation.

For those patients who are discontinued from PN prior to 7 days due to adequate oral or enteral nutrition may be replaced at the discretion of the Sponsor.

9.3 Analysis Populations

The analysis sets in this study include: the Full Analysis Set (FAS), the Per Protocol Set (PPS), and the Safety Analysis Set. The FAS includes all patients who are randomized to receive either Clinolipid or SOC SO-based lipid emulsion (Intralipid), consistent with the intention-to-treat principle. The PPS includes a subset of patients in the FAS who have Holman Index measurements taken at baseline and at least 1 other time point postbaseline, who have received a minimum of 7 days of ILE treatment, and are without a major protocol violation (i.e. violation that potentially impacts the primary endpoint). The Safety Analysis Set includes all patients that have received treatment (Clinolipid or SOC).

Subgroup analyses of patients by age group (e.g., premature infants born <37 weeks of gestation up to 1 month CA, full-term neonates born \geq 37 weeks of gestation <1 month of age, infants 1 to <12 months of age, children 1 to <10 years of age, adolescent 10 to <18

years of age) and subgroup analyses for neonates according to GA and BW will be conducted.

The primary endpoint analysis and secondary endpoint analyses of liver disease including parenteral nutrition-associated liver disease (PNALD) and the adequacy of nutritional intervention will be conducted for both the FAS and PPS. All safety analyses will be conducted on the Safety Analysis Set.

Infants found to subsequently have baseline EFAD will not be considered to have treatment emergent EFAD and will be analyzed separately from infants with normal baseline EFAD status. Unblinded infants will be analyzed separately as well.

